### 6.7.2.2. Overall Survival

**Overall Survival (OS):** OS duration is measured from the date of randomization of any study drug to the date of death from any cause. For each patient who is not known to have died as of the data-inclusion cutoff date for a particular analysis, OS will be censored for that analysis at the date of last contact prior to the data inclusion cutoff date (contacts considered in the determination of last contact date include AE date, lesion assessment date, visit date, and last known alive date).

The final analysis of OS will be conducted together with the analysis of PFS at study completion. Overall survival, 1-year survival rate and 2-year survival rate by treatment will be analyzed for each cohort.

Kaplan-Meier method and the stratified Cox proportional hazard model will be applied.

### **6.7.2.3. Objective Response Rate, Disease control Rate, and Clinical Benefit Rate**

Objective response rate (ORR), disease control rate (DCR), and clinical benefit rate (CBR) are summary measures of best overall response (BOR) as defined by RECIST v1.1. BOR is derived from time point responses. All time point responses observed while on study treatment and during the short term follow up period (but before the initiation of post discontinuation therapy) will be included in the derivation. The one exception includes patients who receive surgery and/or radiotherapy for locally advanced breast cancer. For these patients, only those time point responses occurring prior to surgery/radiotherapy will be included in the derivation.

Each patient's BOR will be categorized as CR, PR, SD, progressive disease (PD), or not evaluable (NE). For patients with bone-only nonmeasurable disease (see Section 6.4.2), BOR will be limited to CR, SD, PD, and NE. Patients with SD will be further classified as SD  $\geq$  6 months or SD < 6 months. Stable disease  $\geq$  6 months includes all patients with a best response of SD and a PFS time of  $\geq$  6 months. A BOR of CR or PR will not require confirmation.

**Objective Response Rate (ORR):** The objective response rate is the percentage of patients with a BOR of CR or PR.

**Disease Control Rate (DCR):** The DCR is the percentage of patients with a BOR of CR, PR, or SD.

**Clinical Benefit Rate (CBR):** The CBR is the percentage of patients with a BOR of CR or PR, or SD for at least 6 months.

For each cohort, the ORR, DCR, and CBR of each treatment arm will be calculated using the ITT population. All rates will be compared between treatment arms within the cohort based on a normal approximation for the difference between the rates.

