### 6.7.1. Primary Endpoint: Progression Free Survival of Cohort A

#### 6.7.1.1. Definition

The primary efficacy measure is progression-free survival of cohort A as defined by RECIST Version 1.1 and determined by the investigator. The PFS time is measured from the date of randomization to the date of objective progression or the date of death due to any cause, whichever is earlier.

If a patient is not known to have progressed or died at the time of analysis, PFS time will be censored at the last known progression-free assessment. The detailed censoring rules are described in the table below (Table JPBQ.6.1).

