**Table JPBQ.6.1. Rules for Determining Date of Progression or Censor for Progression-Free Survival**

Rule	Situation	Date of Progression or Censor	Outcome
1	No baseline tumor assessments	Date of Randomization	Censored
2	No post baseline assessments and no death	Date of Randomization	Censored
3	No documented progression and no death (with a post-baseline tumor assessment)	Date of last adequate tumor assessment	Censored
4	Patient lost to follow-up (or withdrew consent from study participation) before documented progression or death	Date of last adequate tumor assessment	Censored
5	Documented progression	Date of documented progression. If a tumor assessment was done on multiple days, use the earliest date for that visit.	Progressed
6	Death without documented progression	Date of death	Progressed
7	Documented progression or death after missing $\geq 2$ consecutive post-baseline tumor assessments	Date of last adequate tumor assessment before missed assessments or date of randomization, whichever is later	Censored

Note: Progression-free survival and associated outcome is determined by the earliest of the dates above, if more than 1 situation applies.

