### **6.7.3. Sensitivity Analyses**

In order to evaluate the robustness of the primary and key secondary analysis, PFS analysis will also be conducted based on the PP population.

In addition, the following sensitivity analyses will be performed for PFS based on ITT population:

**Progression-Free Survival Sensitivity Analysis 1** (censoring for receiving subsequent systemic anticancer therapy): if a patient is initiated on another anticancer therapy prior to objective progression, including any postdiscontinuation treatment systemic therapy, radiotherapy, or surgical intervention, PFS will be censored at the date of the last complete objective progression-free disease assessment before initiation of the new therapy.

**Progression-Free Survival Sensitivity Analysis 2** (nonobjective progression as a PFS event): if a patient is discontinued from study treatment due to investigator determined non-objective progression (for example, symptomatic deterioration), then the patient's PFS time will be calculated using the date of non-objective progression as the progression date.

**Progression-Free Survival Sensitivity Analysis 3** (forward-dating progressions at unscheduled assessments): if a patient has objective progression at an unscheduled disease assessment, then the PFS time for that patient will be forward-dated to the next scheduled disease assessment.

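### Stable disease of at least 6 months is timed with a PFS that runs on through new anticancer therapy, although best response stops there, so CBR can credit another treatment's disease control to the assigned arm

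*SAP*

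**What the plan says.** SAP 6.7.2.3 builds BOR from time point responses on study treatment and in short-term follow-up, "but before the initiation of post discontinuation therapy". For patients who have surgery or radiotherapy for locally advanced disease, "only those time point responses occurring prior to surgery/radiotherapy will be included in the derivation".

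The section then splits SD at 6 months. The longer category "includes all patients with a best response of SD and a PFS time of" 6 months or more. CBR uses that category: "The CBR is the percentage of patients with a BOR of CR or PR, or SD for at least 6 months". CBR is calculated on the ITT population and compared between arms within each cohort.

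The PFS time comes from SAP 6.7.1.1: "The PFS time is measured from the date of randomization to the date of objective progression or the date of death due to any cause" (the first of the two counts). None of the seven rules in Table JPBQ.6.1 mentions new anticancer therapy. Such censoring appears in two other places:

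- PFS Sensitivity Analysis 1 (SAP 6.7.3): "PFS will be censored at the date of the last complete objective progression-free disease assessment before initiation of the new therapy".
- DoR (SAP 6.7.2.4), which takes over the PFS rules and adds censoring at the last response evaluation before post-discontinuation therapy.

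Neither is linked to SD of 6 months or more, or to CBR.

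**The concern.** Two parts of one endpoint stop at different times. The label SD is fixed from data before any new therapy. The duration that turns SD into clinical benefit can be earned on scans made under a different treatment. Responders are treated differently: their duration stops at new therapy. The SAP gives no reason for the contrast.

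CBR is a named secondary endpoint with a between-arm comparison in each cohort. As written, it does not measure disease control on the assigned regimen, which is what the BOR cut-off suggests is intended.

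**Working it through.** The documents state no CBR rate, sample size or power, so there is no figure of the plan's to reproduce. The check has three steps.

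**1. Can the situation arise under the plan?** Protocol 10.1.2 has sites continue tumour assessments about every 8 weeks (every 12 weeks after 18 months) in patients who stop without objective progression, and record the anticancer therapies they start. With scans continuing, rule 7 of Table JPBQ.6.1 (two or more missed assessments) does not apply. A patient without progression or death is censored at her last adequate assessment, whatever she is then taking.

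**2. Can scans under a new therapy decide the classification?** SAP 6.1.2 sets one month at 365/12 days:

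- 6 months = 6 x 365/12 = 182.5 days.
- Protocol 10.1.1 places scans in the last 7 days of every second 28-day cycle. The nominal window for cycle c is day 28c - 6 to day 28c.
- Cycle 6: days 162-168. Cycle 8: days 218-224.
- PFS runs from randomisation, and the first dose should follow within 7 days (Protocol 9.3). The latest nominal Cycle 6 scan is then day 168 + 7 = 175, still short of 182.5.

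On the nominal schedule, the Cycle 6 scan cannot establish 6 months and the Cycle 8 scan can. Take a patient with SD at week 8 who stops without progression, starts another agent in month 3 and progresses in month 7. Her PFS is 7 x 365/12 = 212.9 days. Her BOR is SD, her PFS time exceeds 182.5 days, and she counts as clinical benefit.

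**3. How large could it be?** Let q be the share of an arm with BOR of SD that starts new therapy before 6 months without progression. Let r be the share of those whose PFS still reaches 6 months. The overstatement of that arm's CBR is q x r. The documents give neither value, so both are assumed:

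| q | r = 0.5 | r = 0.7 | r = 0.9 |
|---|---|---|---|
| 2% | 1.0 points | 1.4 | 1.8 |
| 5% | 2.5 | 3.5 | 4.5 |
| 10% | 5.0 | 7.0 | 9.0 |

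With the planned Cohort A arms (SAP 5.2), this is 2 to 18 of 200 patients on abemaciclib, or 1 to 9 of 100 on placebo.

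The shift in the arm difference is r x (q on abemaciclib - q on placebo). With r = 0.7:

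- 10% against 3%: 0.7 x 7 = +4.9 points.
- 3% against 10%: -4.9 points.
- 5% in both arms: 0.

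For scale, the standard error of the Cohort A difference is sqrt(0.6 x 0.4/100 + 0.6 x 0.4/200) = 6.0 points if CBR is 60% in both arms. It is sqrt(0.65 x 0.35/100 + 0.75 x 0.25/200) = 5.7 points at 65% on placebo and 75% on abemaciclib. These CBR levels are also assumptions.

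**The case against.** The strongest defence is that the rule is explicit and deliberate. It uses the primary ITT PFS time, and not censoring at new therapy is a legitimate treatment-policy choice. It also does not contradict the protocol, whose CBR definition (Protocol 10.1.4) has no new-therapy rule. This stands for primary PFS, which needs no change. It does not explain a CBR whose response component excludes data after new therapy while its duration component includes them, beside a DoR that is censored there.

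The second defence is that the effect is narrow. Only patients with SD who start new therapy before 6 months without objective progression, and who keep being scanned, are affected. CBR is one of several other secondary endpoints and has no allocated alpha. All of that is correct and limits the weight of the point.

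A reader might go further and infer that the rule favours abemaciclib, because toxicity would lead more of those patients to stop without progression. The documents do not support that:

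- They give no rate of new therapy before progression in either arm.
- Toxicity is largely managed by dose suspension and reduction (Protocol Table JPBQ.9.2). A patient who must stop blinded drug may stay on her endocrine therapy (Protocol 9.4.1.1.1.1), in which case no other treatment's effect is being credited.
- SAP 6.7.3, Sensitivity Analysis 2, provides for patients stopped for non-objective progression. They too may start new therapy without objective progression, possibly more often on placebo, which would raise placebo CBR instead.

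A net bias of stated size and sign would therefore be conjecture.

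**Conclusion.** The inconsistency is real on the text as written. SD of 6 months or more can be reached under another anticancer therapy and is then credited to the assigned arm. This can overstate CBR in either arm. The 1 to 9 points per arm hold only under the assumed q of 2-10% and r of 50-90%. The shift in the arm difference may be positive, negative or nil. ORR and DCR rest on BOR alone and are unaffected, as are primary PFS and its test. The point merits a short clarification while the SAP can still be amended. It does not threaten the trial's main conclusion.

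**What to change.** In SAP 6.7.2.3, define SD of 6 months or more as a BOR of SD, a PFS time of at least 6 months, and no post-discontinuation anticancer therapy started before 6 months (182.5 days) from randomisation. This brings CBR into line with the BOR and DoR cut-offs. Report CBR under the current definition as a sensitivity analysis.

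The start date of new therapy is a better criterion than Sensitivity Analysis 1 censoring. That analysis goes back to the last complete assessment before the new therapy. A patient with SD who starts new therapy on day 200 would be censored at her Cycle 6 scan (nominal day 162-168) and scored as under 6 months, although she had passed 182.5 days before the switch. It would also take in surgery that Protocol 9.6.1 permits within study participation. Because BOR stops at such surgery or radiotherapy while PFS time continues, the SAP should also state how SD duration is counted for those patients.

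The cost is one or two sentences and a flag from therapy data already collected under Protocol 10.1.2. CBR may be slightly lower. One small dependence remains: for a patient who switches between day 182.5 and her next scan, the scan that establishes 6 months may fall after the switch.

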## 5.2. Determination of Sample Size

The study plan is to enroll approximately 450 patients in total, with 300 HR+, HER2- locoregionally recurrent or metastatic breast cancer patients who have not received prior endocrine therapy in Cohort A and 150 HR+, HER2- locoregionally recurrent or metastatic breast cancer patients in Cohort B. Assuming approximately 10% screening failure, the study will enter approximately 500 patients.

The approximate 300 patients qualified for Cohort A will be randomized in a 2:1 ratio to Arm A1 (abemaciclib plus NSAI; 200 patients) and Arm A2 (placebo plus NSAI; 100 patients). Patients will be randomized using the following stratification factors: nature of disease (visceral metastases vs. non-visceral metastases) and prior (neo)adjuvant endocrine therapy (prior therapy

with disease-free interval > 12 months from completion of treatment vs. prior therapy with disease-free interval ≤ 12 months from completion of treatment vs. no prior therapy).

A 2-look group-sequential design of the primary endpoint will be used to accommodate an event driven plan for the interim and primary PFS analyses (see protocol Section 12.2.6 for details). The primary PFS analysis will be performed after approximately 170 PFS events in Cohort A have occurred (ie, approximately 43% censoring rate). Assuming a hazard ratio of 0.626, this sample size yields at least 81.4% statistical power to detect superiority of the abemaciclib plus NSAI arm over the placebo plus NSAI arm with the use of a 1-sided log-rank test and a type I error of 0.025. If the true median PFS for the placebo plus NSAI arm is 14.4 months, then the hazard ratio of 0.626 amounts to an approximately 8.6-month (59.7%) improvement in median PFS for the abemaciclib plus NSAI arm under an additional assumption of exponential survival distribution.

Approximately 150 patients will be randomized in a 2:1 ratio to Arm B1 (abemaciclib plus fulvestrant; 100 patients) and Arm B2 (placebo plus fulvestrant; 50 patients). Patients will be randomized using the following stratification factors: nature of disease (visceral metastases vs. non-visceral metastases) and sensitivity to endocrine therapy (primary resistance vs. secondary resistance).

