## 6.7. Efficacy Analyses

For cohort A, the stratification factors for the analysis of primary and secondary analyses are:

- nature of disease (visceral metastases vs non-visceral metastases)
- prior (neo)adjuvant endocrine therapy (prior therapy with disease-free interval  $>12$  months from completion of treatment vs. prior therapy with disease-free interval  $\leq 12$  months from completion of treatment vs. no prior therapy).

For cohort B, the stratification factors for the analysis of primary and secondary analyses are:

- nature of disease (visceral metastases versus non-visceral metastases)
- sensitivity to endocrine therapy (primary resistance versus secondary resistance).

The stratification factors are captured in the IWRS and on eCRFs. Unless otherwise specified, all stratified analyses will be based on the stratification factors per eCRF. A cross tabulation of the frequency of each level of each stratification factor per IWRS and eCRF will be produced.

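### ORR, DCR and CBR are compared with no stratification stated; after stratified randomisation this makes the reported SE and CI somewhat too wide if the factors are prognostic

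*SAP*

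**What the plan says.** SAP 6.7 opens with one factor list per cohort: "For cohort A, the stratification factors for the analysis of primary and secondary analyses are" nature of disease (2 levels) and prior (neo)adjuvant endocrine therapy (3 levels), and "For cohort B, the stratification factors for the analysis of primary and secondary analyses are" nature of disease (2 levels) and sensitivity to endocrine therapy (2 levels). That makes 6 and 4 cells. It adds: "Unless otherwise specified, all stratified analyses will be based on the stratification factors per eCRF".

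ORR, DCR and CBR are secondary endpoints (SAP 4.2). SAP 6.7.2.3 sets the population, "For each cohort, the ORR, DCR, and CBR of each treatment arm will be calculated using the ITT population", and the method, "All rates will be compared between treatment arms within the cohort based on a normal approximation for the difference between the rates". Protocol 12.2.7.3 gives the same method. Neither mentions strata, weights, or a pooled or unpooled variance.

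Elsewhere the SAP says so when it wants stratification: the log-rank test in 6.7.1.2, the Cox models for PFS in 6.7.1.3.1 and 6.7.2.1, and for OS "Kaplan-Meier method and the stratified Cox proportional hazard model will be applied".

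**The concern.** The factors were used to randomise, and Protocol 8.2 gives better power of the analyses as one reason for stratifying. The crude variance of a difference in proportions still includes the between-stratum variation that stratified allocation has removed from the estimate. If the factors predict response, the reported SE and CI are wider than they should be and the test loses some power.

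For ORR there is a reason within the SAP to expect some association. Under 6.7.2.3, patients with nonmeasurable bone-only disease cannot be scored PR, yet they stay in the ITT denominator. By the definition of visceral disease in 5.1 they all fall in the non-visceral stratum, which lowers its ORR. As an illustration, assume 30% to 50% of that stratum is bone-only with almost no responses and everyone else responds at 45%. The strata then differ by 0.30 × 45 = 13.5 to 0.50 × 45 = 22.5 points. This argument does not carry over to DCR or CBR.

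The text is also incomplete for programming: crude or stratified, and which variance, is left to the reader.

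**Working it through.** **Inputs from the documents.** Cohort A 200 vs 100 and Cohort B 100 vs 50, both 2:1 (SAP 5.2). Two-sided 0.05 for tests without their own level (SAP 6.1), which is 2.5% one-sided.

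**Inputs assumed.** Control response 33.3% (the single-agent Phase 1 ORR in the Protocol synopsis, used only as an anchor), a 15-point treatment difference, and two equal strata whose rates differ by a gap g. The documents give no on-study rates, no rates by stratum and no stratum sizes.

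**The plan's own figure.** None is given for these endpoints. As a check on the design inputs, the stated PFS power reproduces. The fixed-design value is Φ(|ln 0.626| × √(170 × 2/9) − 1.96) = Φ(0.92) = 82.1%. With the stated boundaries 0.0082 and 0.0223 it is 81.4%, as in SAP 5.2.

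**Step 1: the SE.** Crude SE = √[p1(1−p1)/n1 + p0(1−p0)/n0]. For Cohort A this is √[0.483 × 0.517/200 + 0.333 × 0.667/100] = √0.003471 = 0.0589. With two equal strata and a common risk difference, the stratified variance replaces each p(1−p) by p(1−p) − (g/2)². At g = 0.20 this gives √[(0.2497 − 0.01)/200 + (0.2222 − 0.01)/100] = √0.003321 = 0.0576.

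| Gap between strata | A: SE | A: 95% half-width, points | B: SE | Change in SE |
|---|---|---|---|---|
| 0 (equals crude) | 0.0589 | 11.55 | 0.0833 | 0 |
| 10 points | 0.0586 | 11.48 | 0.0829 | −0.5% |
| 20 points | 0.0576 | 11.29 | 0.0815 | −2.2% |
| 30 points | 0.0560 | 10.97 | 0.0791 | −5.0% |
| 40 points | 0.0536 | 10.50 | 0.0758 | −9.1% |

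For rates nearer DCR (80% vs 90%, Cohort A) the SE falls by only 0.2% to 2.1% for strata 5 to 15 points apart.

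**Step 2: is true precision lost?** This was simulated with 40,000 trials per scenario and stratified 2:1 allocation. The assumed splits were nature of disease 60/40, prior endocrine therapy 40/30/30 in A and sensitivity 30/70 in B, with small shifts for the second factor. In Cohort A with a 20-point gap, the crude and stratified estimates have the same true SD, 0.0574. The crude method reports 0.0587 and the stratified one 0.0575. At 40 points the true SD is 0.0537 for both, and the crude method still reports 0.0587. In Cohort B at 40 points the figures are 0.0755 true and 0.0827 reported. So the estimate is as good either way; only its stated uncertainty is wrong.

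**Step 3: type I error (one-sided, nominal 2.5%).** The crude Wald test with unpooled variance rejects about 2.9% to 3.1% of the time when the factors are weak, 2.5% (A) and 2.8% (B) at a 20-point gap, and 1.9% in both cohorts at 40 points. The CMH test stays at 2.3% to 2.6%. A stratified Wald test does not cure the excess: it gave 2.7% to 3.0%. The excess therefore comes from the Wald form, and the form of the stratified test matters.

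**Step 4: power.** Putting the stratified SE into the same Wald form moves Cohort A power from 72.1% to 72.6%, 74.0%, 76.4% and 80.0% at gaps of 10, 20, 30 and 40 points. The CMH test gains less, because it also removes the Wald excess. At 20 points it gives 72.4% vs 72.7% crude in A and 43.3% vs 43.9% crude in B. At 30 to 40 points the gain is about 1 to 5 points.

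**The case against.** The strongest reply is that this is a preference and that nothing in the plan is wrong.

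- **No contradiction.** A reader might infer that SAP 6.7 obliges every secondary comparison to be stratified, so that 6.7.2.3 breaks it. The text does not support that. The list fixes which factors, from which source, serve the analyses that are stratified. The plan also treats rates alike: the Kaplan-Meier PFS rates in 6.7.1.3.1 use the same normal approximation. Moreover, a Mantel-Haenszel difference is itself a normal approximation, so a crude method is inferred from silence. This stands.
- **No precision thrown away.** A reader might infer that the crude estimate is less precise. Step 2 shows that it is not, because allocation is already stratified on the same factors. Nor would stratifying the analysis remove imbalance in other variables within strata. This stands.
- **Cohort B sample size.** A reader might infer that the normal approximation fails with 50 controls. Exact coverage of the plain 95% interval at 100 vs 50 is 94.3% for 48% vs 33%, and 93.9% to 94.5% for eight other pairs of rates. That shortfall is minor.
- **Little depends on it.** These are other secondary endpoints with no sample-size basis. Confirmatory alpha is specified only for Cohort A PFS, and even Cohort B PFS tests are descriptive (SAP 6.7.2.1). This also stands.

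What the reply does not answer is that the crude SE is wrong for the randomisation used whenever the factors are prognostic, and that the text does not settle which method is meant.

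**Conclusion.** The point holds as a small improvement to the analysis and a clarification. ORR, DCR and CBR are compared with no stratification stated, although the factors are named and used to randomise. The consequence is a reported SE and CI that are too wide by an amount that depends on how prognostic the factors are: nothing if they are not, about 2% at a 20-point gap, and 5% to 9% only at 30 to 40 points. With weak factors, a plain Wald test is slightly anti-conservative. Power is essentially unchanged up to 20 points.

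All sizes rest on the assumed 33.3% control rate, 15-point effect and stratum patterns. The type I error figures also assume an unpooled variance, which the SAP does not specify. The documents support neither bias, nor loss of true precision, nor an internal contradiction, nor any effect on the primary analysis.

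**What to change.** In SAP 6.7.2.3, state that ORR, DCR and CBR are compared within each cohort by a CMH test and a Mantel-Haenszel risk difference. Use that cohort's two factors per eCRF, in line with SAP 6.7, and give a score-type CI (for example a stratified Miettinen-Nurminen interval). Fix in advance a rule for sparse strata, for instance stratifying by nature of disease alone if a cell is empty or very small in one arm. This matters mainly in Cohort B, where 50 controls over 4 cells average 12.5 per cell (Cohort A: 100 over 6, about 17). Keep the crude rates by arm as descriptive output. If the sponsor prefers the crude comparison, one sentence should say so and name the variance form.

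The cost is a few SAP sentences and standard software. Protocol 12.2.1 lets minor modifications and clarifications be made in the SAP before the sponsor is unblinded to the aggregate database; after that, the change belongs in the clinical study report. The statistical downside is small: sparse cells, and slightly lower power when the factors are not prognostic.
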